#### **3.5.1 INTERNAL STATE VISUAL ANALOG SCALES**

*Hunger and satiety assessments.* At various points over their inpatient admission and outpatient follow-up visit, subjects will be asked to complete a survey to identify their perception of hunger (i.e., visual analog scale [VAS]) [42]. More specifically, the VAS survey will consist of four questions: 1) "How hungry do you feel right now?" 2) "How full do you feel right now?" 3) "How much do you want to eat right now?" and 4) "How much do you think you can eat right now?" Below each question on the survey there is a horizontal 100mm line with qualifying statements such as "Not at all"/"The least I can possibly" and "Extremely"/"The most I can possibly", anchoring the line on the extreme left and right side, respectively. In response to each question, subjects will be asked to digitally draw a vertical mark on the horizontal line to represent the magnitude of their response to the question. A value for each response is quantified by measuring the distance of their mark (in mm) relative to the left end of the line. Therefore, the values (or "scores") for each question range from 0 to 100.

*Intensity assessments.* In order to assess participants' interoceptive awareness of their GI sensations, participants will also be asked to rate the intensity of their overall sensations in their

stomach in relation to four specific stomach sensations: hunger, fullness, pain, and nausea. At various points over their inpatient admission and outpatient follow-up visit, a computerized VAS will be presented on a computer tablet, and participants will use a finger to slide a bar across the scale to indicate their subjective experience. The scales are anchored from 0 (*No Sensation*) to 100 (*Extremely Intense Sensation*).

### **3.5.2 LIKING & WANTING**

Subjects will complete the Liking and Wanting computer assessment. The liking and wanting procedure comprises two tasks designed to assess (1) explicit liking and wanting, followed immediately by (2) implicit wanting for the same target food stimuli [43, 44]. The separate task elements will be integrated to fully randomize explicit and implicit trials. Experiment generator software (E-prime v2.0) is used to integrate the single stimulus trials for the liking task with the paired stimuli trials for the wanting task. Food stimuli presented in the procedure are selected from a database of photographic stimuli and sorted according to their fat content and taste properties into one of four separate categories: high-fat savory (HFSa); low-fat savory (LFSa); high-fat sweet (HFSw); and low-fat sweet (LFSw). Each category is represented by four different foods; hence a total of 16 different food stimuli will be presented in the procedure.

The aim of the explicit task is to obtain introspective hedonic measures for the same stimuli used in the implicit wanting task. Therefore, each food stimulus is assessed independently using visual analogue scales (VAS). The explicit computer task trials consist of 16 food stimuli presented one at a time and rated according to a 100-mm VAS anchored at each end by the statements “not at all” and “extremely”. Subjects will be prompted with the statements “How pleasant would it be to taste some of this food now?” and “How much do you want some of this food?” Responses on the software will be recorded online and mean ratings for each food category (HFSa, LFSa, etc.) are automatically computed.

Implicit wanting is measured by a behavioral “forced choice” methodology. In this task, a food stimulus from one of the four food categories is paired with one stimulus from the remaining categories to form a series of 96 trials in which the subjects will be given the standardized instruction to select the food they “most want to eat now”. In addition to recording the frequency of selections made in each category (with a possible range of 0–48), which may reveal a relative preference, reaction time (in milliseconds) of each choice is also measured. By covertly recording reaction time, subjects will be unaware of implicit changes in their behavior on the task, while remaining free to determine the direction of their choices.

### **3.5.3 DELAY DISCOUNTING**

People generally prefer immediate rewards over delayed rewards, even when the delayed reward has a higher value. The degree to which delayed rewards are discounted in comparison to immediate rewards may provide an index of impulsive decision-making. It has been reported that obese individuals may have difficulty adhering to diets because the long-term rewards of weight loss are strongly discounted when compared to immediate rewards, such as palatable food [45].

We will implement delay discounting computer procedures using an image of a food that scored highly on each individual’s liking scale. This food image will be presented along with a forced choice statement such as “Would you rather eat this food now or receive \$10 tomorrow?” The subject must select either the “food” or “money” option. We will also measure how long it takes to make each selection. The same food image will always be used as the hypothetical subject-specific reward, but hypothetical monetary choices will vary in the amounts of: \$1, \$5, \$10, \$20,

\$50, \$100 and the associated delay times will vary from: now, 4 hours, tomorrow, 1 week, 2 weeks, and 1 month.

Experiment generator software (E-prime v2.0) will be used to present the paired stimuli trials and will be programmed to center the cursor between each trial to produce more consistent response times.

### **3.5.4 EYE TRACKER**

The ISCAN® ETL-300 Eye Tracking device provides detailed measurements about what people look at when they are presented with a visual stimulus, such as a picture of food. Depending on availability of equipment and scheduling of computer tasks, we may use this commercially available device to measure eye gaze duration, eye direction, pupil dilation, and spontaneous eye blink during the various computer tasks. As spontaneous eye blink rate has been cited as a non-invasive measure of resting dopamine release, particularly in the striatum [46], we may film subjects' eye movements at rest before and after some scanning sessions. These measurements will help us better understand the psychological factors underlying the subject's choices during the various computer tasks.

The eye tracking device can be used with contact lens or glasses. The subject's eyes are viewed using a specialized miniature infrared video camera system embedded in the headgear. A second video imaging system captures the scene that the subject is viewing. A 25-foot tether will connect the head-mounted device to a computer for data storage and analysis. Resting eye blink data will be acquired at approximately 6-minute intervals. Pilot data collected using the eye-tracker have found that the device is comfortable for subjects to wear during the computer tasks and provides implicit measures in addition to the explicit measures collected during the tasks.

### **3.5.5 FOOD AND NEUTRAL OBJECT Go/No Go**

Subjects will complete a Go/NoGo task, a well-validated behavioral measure of impulse control. In this task, subjects will be asked to press a button in response to target foods and withhold a response for non-target images. The order of target foods will be counterbalanced. We will use palatable (high fat/high energy; (e.g. macaroni and cheese, French fries, ice cream, cookies), less palatable (low fat/low energy; e.g., grilled chicken, yogurt, pickles, salad) and non-food targets (e.g., toys displayed on round disks) that are equated in complexity and spatial frequency to the food stimuli. In each run, subjects will be presented with a stimulus for 500 milliseconds followed by a variable inter-stimulus interval (ISI) of 2 to 4 seconds. Target stimuli will appear on 75% of the trials to build up the prepotent response pattern. Non-targets will appear the other 25% of the time and will be parametrically manipulated in order to compare non-target trials following 1, 3, or 5 target trials as in Durston et al. [47], where it was shown that, as the number of preceding target trials increases, response inhibition to non-targets becomes increasingly difficult. Participants will be given a 3-minute practice to ensure they understand and can follow the directions, followed by 192 trials (12 minutes). Outcome variables are reaction time, hit rate and false alarm rate.

### **3.5.6 SLIPS-OF-ACTION PARADIGM**

We will use a validated version of the slips-of-action paradigm to assess subjects' reliance on goal-directed ('action-outcome') versus habit ('stimulus-response') learning [48, 49]. Goal-directed behaviors are guided by the assessment and valuation of possible outcomes. Thus, if the

outcome of a certain behavior is devalued, the behavior is less likely to be performed. Habit responding occurs when an individual's actions are driven by external stimuli, which trigger an automatic behavioral response. This task assesses such learning in three stages: control discrimination training, congruent discrimination training, and an incongruent conflict task.

In the initial stage, subjects will be presented with a cue (a box) with instructions to either "Press Left" or "Press Right." If the subject responds correctly, they will receive a reward (i.e., the box will open, revealing an image that is worth points). Following 4 practice trials, the subject will begin the next set of practice trials, where they will need to learn the correct key for the reward. Subjects will respond with either "Left" or "Right" presses. Subjects are instructed to try to win as many points as possible by responding as quickly and accurately as possible. Incorrect responses and those made after 2s will result in 0 points. This type of discrimination should be soluble by both the goal-direct and habit system.

For the second stage, two open boxes containing different icons will appear on the screen for 4 practice trials. One box will be covered with a red cross, indicating that the previously correct response is no longer associated with a reward. Subjects will be told to only respond by pressing the key that is associated with a valued image. No feedback will be provided for correct or incorrect responses. During the test trials, icons will be replaced with various new icons, and subjects must learn the correct keys as they did in the practice session. This stage of the task should be controlled predominantly by a goal-directed system.

The third stage features a conflict between the previously associated cues and outcomes. For this discrimination, the cue and outcome status of stimulus pairs has been reversed. These pairings force the subject to rely on stimulus-response learning to solve the cue-outcome incongruent discrimination. This task will be completed in ~ 72 test trials, presented in 6 blocks with an 8 second inter trial interval. Subjects will view each cue for 1s with a 2 – 2.5s response window. Including practice trials, total task time will be 27 minutes.

### 3.5.7 REWARD PREDICTION ERROR

We will use a computerized probabilistic procedural learning task, the Probabilistic Selection Task, to assess participants ability to learn from both positive and negative outcomes [50]. Dopamine plays a key role in reinforcement learning. Learning from positive outcomes is thought to be a result of phasic bursts firing of dopamine which stimulates the D1R direct ("Go") pathway and inhibits the D2R indirect pathway ("Stop"). The dip in dopaminergic firing experienced as a result of negative outcomes is thought to support learning to avoid the unrewarded choice. This task trains participants on reward contingencies and then tests their learning strategy to determine whether they are more adept at learning predominantly from positive feedback (suggestive of high phasic dopamine response) or from negative outcomes (suggestive of sufficient degree of dip in phasic and tonic dopamine response).

In the training phase of the task, participants will learn via feedback to select one of two stimuli across 3 stimulus pairs presented randomly. Among each pair of stimuli (AB, CD, EF), feedback as to the correct stimulus is given in a probabilistic manner. Among pair AB, stimulus A will be "correct" 80% of the time and thus stimulus B will be the "incorrect" choice during 80% of forced choices (but conversely, stimulus B will be the "correct" choice during 20% of the trials). The probability distinction between correct and incorrect choices is made less stark with stimuli C and E, which are the correct choices 70% and 60% of the time, respectively. As described by Frank et al. (2004), participants will learn to choose stimuli A, C and E, more often than their counterparts

B, D, and F during training. Participants will train to criterion (65% A in AB, 60% C in CD, 50% E in EF) prior to advancing to the next phase [51].

To determine whether this learning was accomplished predominantly by learning to select A, C, or E (positive feedback) or to avoid B, D, or F (negative feedback), participants are subsequently tested using novel stimuli pairs without feedback. During this phase, participants are asked to select the stimulus that is most likely to be “correct” based on what they learned from training. Based on an analysis by Cox et al. (2015), positive feedback learning will be assessed via percentage of novel combination trials where patterns A and C were selected (A>CDEF + C>EF) while negative feedback learning will be assessed via percentage of trials where B and D were avoided (B<CDEF + D<EF). Both phases of the task combined last approximately 25 minutes.

### **3.6 Taste preferences and food intake**

In order to investigate the associations between brain dopamine D2BP, food perception and preference and food intake, participants will complete a taste paradigm focusing on fat and sweet preference/perception as well as an *ad libitum* food array during their inpatient visit. Assessments conducted in advance of/during screening visit (as noted) mainly used to confirm eligibility criteria.

#### **3.6.1 FOOD FREQUENCY QUESTIONNAIRE (FFQ) [52]:**

Food Frequency Questionnaire (FFQ) is a self-assessment questionnaire developed to identify foods and macronutrients that significantly contribute to energy intake. Subjects will be given instructions to complete a form, which will be reviewed for completeness by clinic staff and any blank answers will be resolved. The FFQ contains questions on the frequency and portion size of consumption of 100 items over a defined period of time. We plan to use the latest version of the National Cancer Institute Diet History Questionnaire. Completed during screening visit.

#### **3.6.2 PSYCHOPHYSICAL TASTE TEST**

Participants will complete a taste paradigm to determine sucrose detection threshold, as well as sucrose and fat preference levels as follows.

**Above-threshold or Suprathreshold intensity Test:** Suprathreshold intensity testing allows for the assessment of the intensity of a stimulus that is clearly perceptible by the assessor between concentrations of a compound, at a suprathreshold concentration range. GLMS are designed to be more valid than traditional VAS when comparing inter-individual subjective ratings. Subjects will be trained on the use of the general labelled magnitude scale (gLMS) before we measure perceived intensities. Two trials consisting of 4 ascending concentrations of each stimulus with the first “concentration” being water will be presented to the subjects. All four concentrations will be presented in random order without repeat. Subjects will rate the perceived intensity of the stimulus using the gLMS scale and we will use the mean intensities of the two trials at each concentration for each stimulus to evaluate subjects’ taste intensity perception. We will use **0.00, 0.09, 0.35, and 1.05 mol/l** sucrose solutions. The task takes approximately 30 minutes to complete.

**Preference testing:** Sucrose and fat preference will be assessed using a two-series paired comparison-tracking method developed at the Monell Center for Adults [53-55]. Subjects will be presented with pairs of solutions differing in sucrose concentration (3, 6, 12, 24, and 36 g per 100 mL) and pairs of puddings differing in fat concentrations (0, 3.8, 8.4, 19, and 33 percent fat by weight, achieved via dilutions of skim 0% fat and heavy cream 33% fat in commercially available

vanilla pudding powder). They will be asked to taste the samples without swallowing and point to which of the pair they liked better. Subsequently, each pair presented will be determined by the subject's preceding preference choice. The entire task is then repeated with the stimulus pairs presented in reverse order. After completion of the taste task, the geometric mean of the preferred concentrations will be determined. This serves as an estimate of the participant's most preferred level of sweet and fat, separately [56, 57]. The task takes approximately 15 minutes to complete.

To evaluate subjects' ability to detect differences in the amounts of fat and sugar, subjects will sample without swallowing the five solutions differing in sugar concentration during one session and the five puddings that differed in fat during another. Subjects will rinse three times after tasting each sample. After each sample is tasted, they will be asked to rank them from least to most sweet or from least to most creamy, respectively. Subject responses will be scored from 0 to 2, following Stewart et al. [58]. A score of 2 indicated all correct (for example, 3.1, 6.9 and 15.6% wt/wt); a score of 1 indicated one was correct and the other two were adjacent to each other (for example, 3.1, 15.6 and 6.9% wt/wt); and a score of 0 indicated that all were incorrect (for example, 6.9, 15.6 and 3.1% wt/wt).

All taste samples will be kept chilled and brought to room temperature prior to testing. Testing will be performed after at least 2 hours of fasting and last approximately 1 hour.

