## 1.3 Exploratory Aims

1. Investigate the associations between brain dopamine D2BP and neural bases of food perception and preference.
2. Investigate the metabolic and endocrine correlates of brain dopamine D2BP and neural bases of food perception and preference.
3. Investigate the behavioral correlates of brain dopamine D2BP such as free-living physical activity, ad libitum meal consumption, and body weight changes over a one year period.

4. Investigate the psychological correlates of brain dopamine D2BP as determined by various questionnaires and computer tasks.

*With the exception of the neuropsychological procedures completed at screening visit, a number of procedures described in the following text are pertinent to exploratory study aims outlined above. We will make every effort to complete and collect all of these exploratory measures in order to generate hypotheses for future studies. However, for various reasons, it may not be feasible to collect each measure on every participant.*

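### Preferred fat level is scored as a geometric mean although one pudding contains 0% fat, so ending either series on 0% gives a score of exactly 0 whatever the other series gave

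*Combined protocol and SAP*

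**What the plan says.** Section 3.6.2 (Psychophysical Taste Test, preference testing) uses a "two-series paired comparison-tracking method" for both tastes. For sweetness it presents "pairs of solutions differing in sucrose concentration (3, 6, 12, 24, and 36 g per 100 mL"; for fat it presents "pairs of puddings differing in fat concentrations (0, 3.8, 8.4, 19, and 33 percent fat by weight". The zero is a nominal zero and not a small value rounded down, since the range is "achieved via dilutions of skim 0% fat and heavy cream 33% fat".

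After the first run, "The entire task is then repeated with the stimulus pairs presented in reverse order". Then "the geometric mean of the preferred concentrations will be determined", and "This serves as an estimate of the participant's most preferred level of sweet and fat, separately". The same scoring rule therefore covers fat and sucrose.

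Neither Section 3.6.2 nor Section 4 (Statistical Analyses) gives an offset, a substitute value, a rank score or any other rule for the 0% level.

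The introduction to Section 3.6 ties the taste tests to the study of D2BP, food preference and intake. In Section 1.3 the matching aim is exploratory: "Investigate the associations between brain dopamine D2BP and neural bases of food perception and preference".

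**The concern.** A geometric mean suits concentrations that are all positive. The sucrose series starts at 3 g per 100 mL and meets that condition. The fat series starts at 0 and does not.

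With a zero in the set, the score stops being an average. The task is presumably run twice because a single run is noisy, yet whenever one run ends on 0% the other run is discarded. A participant whose two runs disagree is then recorded as identical to one who settled on the fat-free pudding both times.

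What is at stake is the fat-preference score when it is related to D2BP. In a sample planned at 39, or at most 60 (Section 2.1), a few values forced to the floor could move a correlation.

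**Working it through.** The plan reports no figure for this score, so there is none to reproduce. The check follows from the stated levels and the stated rule.

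**Inputs (all from Section 3.6.2).** Fat levels: 0, 3.8, 8.4, 19, 33 percent. Sucrose levels: 3, 6, 12, 24, 36 g per 100 mL. Two series, read as giving one preferred level each, a and b.

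**Formulas.** Geometric mean GM = √(a × b). For comparison, arithmetic mean AM = (a + b)/2, and mean step number with the five levels numbered 1 to 5.

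**Fat, pairs containing 0, with some others for contrast:**

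| Pair (a, b) | GM | AM | Mean step |
|---|---|---|---|
| (0, 0) | 0 | 0 | 1 |
| (0, 3.8) | 0 | 1.9 | 1.5 |
| (0, 8.4) | 0 | 4.2 | 2 |
| (0, 19) | 0 | 9.5 | 2.5 |
| (0, 33) | 0 | 16.5 | 3 |
| (3.8, 3.8) | 3.8 | 3.8 | 2 |
| (3.8, 33) | √125.4 = 11.2 | 18.4 | 3.5 |
| (8.4, 19) | 12.63 | 13.7 | 3.5 |
| (33, 33) | 33 | 33 | 5 |

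**Count.** There are 5 × 5 = 25 ordered pairs. Pairs without a zero: 4 × 4 = 16. Pairs with at least one zero: 25 − 16 = 9, and all 9 score 0. One of these is (0, 0), so 8 have a non-zero partner.

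**Shape of the score.** The smallest non-zero score is 3.8, so no participant can fall between 0 and 3.8. A one-step change in one series, from (0, 33) to (3.8, 33), moves the score from 0 to 11.2. The ordering is affected too: (0, 33) ranks below (3.8, 3.8) under the geometric mean, but above it by arithmetic mean (16.5 against 3.8) and by mean step (3 against 2). Analysing ranks of the stated score would therefore not repair it.

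**Sucrose.** No pair gives 0. Scores run from 3 to 36; for example (3, 36) gives √108 = 10.39. The rule works as intended there.

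**Adding a constant c**, √((a + c)(b + c)) − c, separates the pairs, but the result depends on c, which the documents do not supply: (0, 33) scores 1.72 with c = 0.1, 3.59 with 0.5, 4.83 with 1 and 8.03 with 3.8.

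**The case against.** The strongest case on the other side is about reach, and much of it stands.

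- A reader might infer that choosing the 0% pudding at any moment gives a score of 0. The text does not support that. The task is adaptive, and the mean is taken over the preferred concentrations. A 0% choice in an intermediate pair does no harm if the series ends on another level.
- A reader might infer that mid-range responders in general are coded as fat avoiders. They are not: (8.4, 8.4) or (8.4, 19) score normally. Only participants who end one series on 0% and the other above it are misrepresented, and for (0, 3.8) the distortion is small. For (0, 33) it is fair to say that no single number describes a stable preference.
- A reader might take 9 of 25 as an expected share of participants. It is a count of possible results.
- A reader might object that the logarithm of a zero score does not exist. The plan announces no log transform of the score. This is only a computing caution: software that obtains a geometric mean through logarithms may return a missing value instead of 0.
- The measure enters no primary aim, numbered hypothesis or power calculation. Section 1.3 also accepts that exploratory measures may not be collected on everyone.
- If the preferred level from each series is kept, the score can be recomputed at analysis, so nothing is lost irretrievably.
- Every alternative score has some drawback, so the choice among them is partly judgement.

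None of this rescues the rule as written. The section cites published work for the score, which could not be consulted, but the protocol text itself states the rule and makes no exception for 0%.

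**Conclusion.** The point holds within narrow limits. As written, the fat score is exactly 0 for every participant whose preferred level is 0% in at least one of the two series, and it cannot tell (0, 33) from (0, 0). This is a stated rule that gives a misleading value, not merely a missing detail.

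The arithmetic is exact. It rests on two readings: each series yields one preferred level, and the 0% pudding enters the calculation as 0. How many participants would be affected cannot be derived from the documents; it could be none. The sucrose score, the primary aims and the sample size are unaffected. The correction is worth making because it is certain in its effect and almost free, not because the study's main conclusions depend on it.

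**What to change.** Change one sentence in Section 3.6.2. Keep the geometric mean for sucrose. For fat, state that the preferred level is the arithmetic mean of the two percent-fat values; the mean of the two step numbers (1 to 5) is an acceptable alternative. Choose one and record it before any fat score is examined against D2BP. An added constant is less attractive, because the score would depend on an arbitrary value.

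Cost: the sweet and fat scores will be built on different scales. The arithmetic mean gives the widely spaced upper fat levels more weight, while step numbers treat unequal gaps as equal. Both are small drawbacks in an exploratory measure. Samples and procedure stay as they are, no new data are needed, and participants already tested can be rescored provided that the result of each series was stored.

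### The 0–2 taste-ranking score is worded for three samples, but participants rank five, so it cannot be applied as written

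*Combined protocol and SAP*

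**What the plan says.** In section 3.6.2 of the combined protocol and SAP, the preference test uses five sucrose levels (3, 6, 12, 24 and 36 g per 100 mL) and five fat levels (0, 3.8, 8.4, 19 and 33 percent by weight). To assess discrimination, participants taste "the five solutions differing in sugar concentration during one session and the five puddings that differed in fat during another". After tasting, "they will be asked to rank them from least to most sweet or from least to most creamy, respectively". The recorded response is therefore a full ordering of five samples, once for sugar and once for fat.

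The scoring follows a cited study: "Subject responses will be scored from 0 to 2". A 2 is given when all are correct and a 0 when all are incorrect. For the category between, "a score of 1 indicated one was correct and the other two were adjacent to each other". Each of the three worked examples lists three concentrations (3.1, 6.9 and 15.6% wt/wt in different orders).

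Section 3.6 ties the taste measures to D2BP, food perception and preference, and intake. Section 4 does not mention the ranking score.

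**The concern.** One sample correct plus two others makes three, while the task produces an ordering of five. The middle category is the only one that gives partial credit, and it does not describe any five-sample ranking. The document gives no rule for extending it and does not say which three of the five samples would be scored.

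Without a rule, whoever scores the rankings must devise one. The plausible choices give different scores to the same ranking. If the choice is made after the data have been seen, it becomes an avoidable degree of freedom in the exploratory analysis of taste discrimination against D2BP.

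**Working it through.** The plan states no figure to reproduce, so the check enumerates the possible rankings.

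**Inputs (section 3.6.2).** Five samples per ranking, and the three score definitions. Ties are assumed not to be allowed, so there are 5! = 120 possible orders.

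**Orders by number of samples in the correct place.** The number with exactly k correct is C(5,k) × D(5−k), where D(m) is the number of orders of m items with none in place: D(0)=1, D(1)=0, D(2)=1, D(3)=2, D(4)=9, D(5)=44.

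| Correct | Calculation | Orders |
|---|---|---|
| 0 | 1 × 44 | 44 |
| 1 | 5 × 9 | 45 |
| 2 | 10 × 2 | 20 |
| 3 | 10 × 1 | 10 |
| 4 | 5 × 0 | 0 |
| 5 | 1 × 1 | 1 |
| Total | | 120 |

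**Literal reading.** Score 2 covers 1 order, score 0 covers 44, and score 1 covers none. Unscored: 120 − 1 − 44 = 75, or 62.5% of possible orders.

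**Broader readings of score 1**

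| Score 1 taken to mean | Orders covered | Left unscored |
|---|---|---|
| Exactly one sample in place | 45 | 75 − 45 = 30 |
| One exchange of neighbours, the other three in place | 4 | 75 − 4 = 71 |
| One in place, the other four in neighbouring exchanges | 3 | 75 − 3 = 72 |

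**How particular orders fare** (1 = weakest, 5 = strongest)

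- A single neighbour exchange such as 1-2-3-5-4 has three samples in place and 9 of 10 pairs in the right order, so Kendall's tau = (9 − 1)/10 = 0.8. There are four such orders. They have no score under the literal reading, and none under the exactly-one-in-place reading.
- The complete reversal 5-4-3-2-1 keeps the middle sample in place. Under the exactly-one-in-place reading it scores 1, although tau = −1.
- The order 2-1-4-5-3 has no sample in place and scores 0. Yet 7 of its 10 pairs are correctly ordered, so tau = (7 − 3)/10 = 0.4.

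**Comparison with three samples.** Of 3! = 6 orders, 1 is all correct, 3 have one in place and 2 have none. The rule then covers all 6 if one in place is enough for score 1. It covers 5 of 6 if the other two must be neighbouring levels, because the reversal is left out. The wording therefore nearly or fully covers three samples and breaks down at five.

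**The case against.** The strongest reply is that 75 depends on extending scores 2 and 0 to five samples while refusing to extend score 1. All three scores are illustrated with the same three concentrations, so a strict three-sample reading would cover none of the 120 orders. Extending score 1 to exactly one in place leaves 30, and treating it as any partly correct ranking leaves none. This stands: 75 belongs to one reading and should carry that label. However, the any-partly-correct reading drops the adjacency condition altogether, and the document does not state it or any other extension.

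A reader might infer that most participants, or most nearly correct rankings, would go unscored. The document does not support either. The count weights all orders equally, and nothing suggests that people rank at random. Neighbouring sucrose levels differ by factors of 1.5 to 2 (36/24 = 1.5; 6/3, 12/6 and 24/12 = 2), so many participants may rank all five correctly and receive a 2. Of the 75 orders, 45 have only one sample in place, and only 4 are single neighbour exchanges.

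A reader might also treat the example concentrations, which are not among this study's levels, as a separate error. They are given as examples after a citation and are not claimed to be this study's samples. The cited study is not available here, so whether it has a five-sample version cannot be checked. The mismatch does not depend on that.

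Finally, little turns on the measure. Section 1.3 describes the exploratory measures as hypothesis-generating and says they may not be collected on everyone. Section 4 plans no analysis of this score. That limits the importance of the point but does not make the rule usable.

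**Conclusion.** The point holds as a mismatch within section 3.6.2: the stated score does not fit the stated task. On the literal reading, 75 of 120 possible orders have no score, including the four smallest possible errors. The three broader readings tested leave 30 to 72, and the one leaving 30 rewards a complete reversal above rankings that are mostly right. The figures assume full rankings without ties and describe possible orders only; the share of participants affected cannot be derived from the document. No primary aim or sample size is touched, so this is a minor correction worth making before the rankings are scored.

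**What to change.** Replace the scoring sentences with a rule that gives every five-sample ranking a value: Kendall's (or Spearman's) rank correlation between the participant's order and the true order, computed separately for sugar and for fat.

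If the 0–2 score is to be kept, state before analysis how 0, 1 and 2 apply to five samples, covering all 120 orders. Alternatively, name the three study concentrations to be scored for each of sugar and fat, and define the score for every order of those three.

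The cost is about one sentence and no new data, because the full ranking is already collected; the rankings themselves should be retained. The drawback of the rank correlation is that it is less directly comparable with the cited study's 0–2 score.
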